## 4.1.2. Exclusion Criteria

- 1. Prior treatment with CD47 or SIRPα-targeting agents (with exception of magrolimab for patients in the Rollover Cohort).
- 2. Prior anti-leukemic therapies including, but not limited to, chemotherapy (with the exception of hydroxyurea or oral etoposide), targeted therapies, immunotherapy, or radiotherapy within 4 weeks prior to Day 1 magrolimab dosing. NOTE: Localized non-central nervous system (non-CNS) radiotherapy, previous hormonal therapy with luteinizing hormone-releasing hormone (LHRH) agonists for prostate cancer, and treatment with bisphosphonates and receptor activator of nuclear factor kappa-B ligand (RANKL) inhibitors are not criteria for exclusion.
- 3. **TN/U Cohorts only**: Any prior anti-leukemic therapy (excluding hydroxyurea or oral etoposide), prior treatment with hypomethylating agents and/or low dose cytarabine.
- R/R Expansion Cohort, R/R MDS Magrolimab Monotherapy Cohort, TN/U
   Cohorts, and RBC Transfusion-dependent Low-risk MDS Cohort only:
   Contraindications to azacitidine, including advanced malignant hepatic tumors or known hypersensitivity to azacitidine or mannitol.
- 5. Acute promyelocytic leukemia.
- 6. Known inherited or acquired bleeding disorders.
- 7. Previous allogeneic hematopoietic stem cell transplant within 6 months prior to enrollment, active graft versus host disease (GVHD), or requiring transplant-related immunosuppression.
- 8. Clinical suspicion of active CNS involvement by leukemia.
- 9. Significant medical diseases or conditions, as assessed by the Investigators and Sponsor, that would substantially increase the risk-benefit ratio of participating in the study. This includes, but is not limited to, acute myocardial infarction within the last 6 months, unstable angina, uncontrolled diabetes mellitus, significant active infections, and congestive heart failure New York Heart Association (NYHA) Class III-IV.
- 10. Second malignancy, except treated basal cell or localized squamous skin carcinomas, localized prostate cancer, or other malignancies for which patients are not on active anti-cancer therapy as defined in Exclusion Criterion 2.

- 11. History of psychiatric illness or substance abuse likely to interfere with the ability to comply with protocol requirements or give informed consent.
- 12. Pregnancy or active breastfeeding.
- 13. Known active or chronic hepatitis B or C infection or human immunodeficiency virus (HIV).

# 4.2. Patient Screening and Enrollment Procedures

All patients who enter the screening period for the study, which starts when the patient signs the informed consent form (ICF), receive a unique patient identification number before any study procedures are performed. This number is used to identify the patient throughout the clinical trial and must be used on all study documentation related to that patient, including if a patient is rescreened.

Patient screening laboratory assessments may be repeated beyond the initial screening assessments within the 30-day screening period. Patients who screen fail may undergo repeated screening if the patient's medical condition has changed.

All patients who provide informed consent must be registered in the electronic data capture (EDC) system, including any screen failures.

A patient is defined as enrolled in the study once all eligibility criteria have been satisfied and the Sponsor has approved the cohort or study arm assignment. After signing the ICF, eligible patients are expected to receive the first dose of study treatment (Study Day 1) within 30 days.

## 4.3. Informed Consent Process

All participants must be provided an ICF describing the study with sufficient information for participants to make an informed decision regarding their participation. Participants must sign the Institutional Review Board/Research Ethics Committee (IRB/REC)-approved ICF prior to participation in any study specific procedure. Data from assessments performed as part of SOC prior to ICF signature may be used if they are within the required screening period. The participant must receive a copy of the signed and dated consent documents. A signed copy (in paper or electronic format) of

the consent documents must be retained in the medical record or research file. The first dose of magrolimab is to be given within 30 days of signing the ICF.

# 4.4. Registration Process

Patient will be assigned a patient identification number at the time of consent.

Prior to being assigned a dose cohort or treatment arm, patients must have signed the informed consent and satisfied all of the eligibility criteria. The Investigator and clinical team will determine the eligibility of the patient. Once a patient has been assigned to a dose cohort, they will be considered enrolled.

# 4.5. Contraception Requirements

# 4.5.1. Definition of Childbearing Potential

For the purposes of this study, a female-born patient is considered of childbearing potential following the initiation of puberty (Tanner stage 2) until becoming postmenopausal unless the patient is permanently sterile or has medically documented ovarian failure.

Women are considered to be in a postmenopausal state when they are at least 54 years of age with cessation of previously occurring menses for at least 12 months without an alternative cause.

Permanent sterilization includes hysterectomy, bilateral oophorectomy, or bilateral salpingectomy in a female patient of any age.

# 4.5.2. Definition of Male Fertility

For the purposes of this study, a male-born patient is considered fertile after the initiation of puberty unless the patient is permanently sterile by bilateral orchidectomy or medical documentation.

#### 4.5.3. Female Patients

Female patients of childbearing potential who have a negative serum or urine pregnancy test before enrollment must agree to use 1 of the following highly effective forms of contraception (defined as methods that can achieve a failure rate of less than 1% per year when used consistently and correctly):

- Bilateral tubal occlusion
- Vasectomized partner
- Intrauterine device (IUD)
- Intrauterine hormone-releasing system (IUS)
- Combined hormonal contraception (estrogen- and progestogen-containing)
   associated with inhibition of ovulation (oral, intravaginal, transdermal)
- Progestogen-only hormonal contraception associated with inhibition of ovulation (oral, injectable, implantable)
- Abstinence

Defined as: refraining from heterosexual intercourse for the entire period of risk associated with the study treatments. Periodic abstinence is not acceptable (calendar, symptothermal, post-ovulation methods), nor is the withdrawal method (coitus interruptus), spermicides only, and lactational amenorrhea method. The reliability of sexual abstinence needs to be evaluated in relation to the duration of the clinical trial and the preferred and usual lifestyle of the patient.

Contraception must be effective at the first administration of study treatment (magrolimab or azacitidine), throughout the trial, and for 6 months after the last dose of magrolimab or azacitidine, whichever ends later.

## 4.5.4. Male Patients

A man who is sexually active with a woman of childbearing potential (WOCBP) and has not had a vasectomy must agree to use a barrier method of birth control (e.g., either condom with spermicidal foam/gel/film/cream/suppository or partner with occlusive cap [diaphragm or cervical/vault caps] with spermicidal foam/gel/film/cream/suppository) during the study. A female condom and a male condom should not be used together.

Contraception must be effective at the first administration of study drug (magrolimab or azacitidine), throughout the trial, and for 3 months after the last dose of magrolimab or azacitidine, whichever ends later.

It should be explained to the patient that if his partner is pregnant or breastfeeding when he is enrolled on the trial, the patient should use barrier method contraception (condom) to prevent the unborn fetus or the baby being exposed to investigational product.

Male patients must also refrain from sperm donation and cryopreservation of cells during treatment and until the end of contraception requirement. If needed, male participants should be advised to seek advice about sperm donation and cryopreservation prior to treatment..

## 5. STUDY DRUG INFORMATION

Detailed instructions for magrolimab and azacitidine preparation and handling are provided in the Pharmacy Manual.

# 5.1. Magrolimab

The active pharmaceutical ingredient (API) is magrolimab, a humanized IgG4 monoclonal antibody of the IgG4 kappa isotype containing a Ser-Pro (S-P) substitution in the hinge region (position 228) of the heavy chain to reduce Fab-arm exchange. It comprises a disulfide-linked glycosylated tetramer, consisting of 2 identical 444 amino acid heavy gamma chains and 2 identical 219 amino acid kappa light chains. Magrolimab targets the human CD47 antigen. Magrolimab drug product is a sterile, clear, colorless, preservative-free liquid intended for IV infusion.

Magrolimab API is manufactured under current Good Manufacturing Practices.

Magrolimab is supplied in single-use, 10-mL vials containing 200 mg of the antibody in a formulation of 10 mM sodium acetate, 5% (w/v) sorbitol, 0.01% (w/v) polysorbate 20, at pH of 5.0.

The labeling complies with the requirements of the applicable regulatory agencies.

Vials containing magrolimab should be stored under refrigeration at 2 to 8°C (36°F to 46°F) in an appropriate, locked room and/or locked refrigerator, accessible only to pharmacy personnel, the Principal Investigator, or a duly designated person.

Magrolimab should not be frozen. Protect from light during storage. DO NOT SHAKE.

Additional details about magrolimab are provided in the Pharmacy Manual.

## 5.2. Azacitidine

Azacitidine is a nucleoside metabolic inhibitor. Azacitidine is a white to off-white solid supplied in a sterile form for reconstitution as a suspension for SC injection or (in the US only) reconstitution as a solution with further dilution for IV infusion.

Single-use vials of azacitidine contain 100 mg of azacitidine and 100 mg mannitol as a sterile lyophilized powder.

Storage and handling of azacitidine should follow local prescribing information.

Additional details about azacitidine are provided in the Pharmacy Manual.

## 6. TREATMENT PLAN

## 6.1. Study Drug Administration

Patients should be premedicated in accordance with Section 6.1.3. Magrolimab and azacitidine should be prepared as outlined in the Pharmacy Manual for the study.

The dose of each study drug will be calculated based on actual weight at enrollment (using weight obtained either at screening or on Day 1) and remains constant throughout the study, unless there is a > 10% change in weight from baseline. Modifications to the study drug doses administered should be made for a > 10% change in body weight and according to local and regional prescribing standards. Dose modifications for changes in body weight < 10% may be made according to local institutional guidelines.

Patients may continue study treatment with magrolimab and/or azacitidine until they show evidence of disease progression (treatment failure or relapse after CR/CRi), no

longer derive clinical benefit, or demonstrate unacceptable toxicity (further details about treatment discontinuation in Section 8.1). If the treating physician and Sponsor agree that it is in the best interest of the patient to continue treatment with either magrolimab or azacitidine alone, the patient may continue to participate in the study provided that other protocol stipulations are met.

# 6.1.1. Magrolimab

All patients will receive magrolimab administered IV as described below:

- R/R Cohort (all stages): Magrolimab will be dosed using an intrapatient dose escalation schedule as shown in Table 3-1.
- TN/U Dose Evaluation Cohort: Magrolimab will be given according to an intrapatient dose escalation schedule, with continued weekly dosing after Cycle 2 as shown in Table 3-2.
- TN/U Expansion Cohort (including the MDS Registrational Cohort):
   Magrolimab will be given according to the dose schedule with continued Q2W dosing starting Cycle 3 and thereafter, as shown in Table 3-2.
- TP53 mutant TN/U AML Subcohort: Magrolimab will be given according to an intrapatient dose escalation schedule with continued Q2W dosing starting Cycle 3 and thereafter, as shown in Table 3-2.
- RBC Transfusion-dependent Low-risk MDS Cohort: Magrolimab will be given according to the dose schedule with continued Q4W dosing starting Cycle 2 and thereafter, as shown in Table 3-3.
- Rollover AML Cohort: The Rollover Cohort will receive the dose and schedule of
  magrolimab monotherapy as shown in Appendix F. At the discretion of the CTSC for
  this study, patients who are receiving lower doses may be escalated to the highest
  dose determined to be safe by the CTSC for this study.

The duration of each magrolimab infusion will be 3 hours (± 30 minutes) for the first week of treatment in the R/R and TN/U cohorts. Starting the second week of treatment, the magrolimab infusion will be 2 hours (± 30 minutes). The reduced infusion time to 2 hours is utilized based on prior data demonstrating majority CD47 RO on peripheral blood cells, thus mitigating anticipated RBC toxicities from magrolimab.

Magrolimab doses given twice weekly are to be at least 24 hours apart, with a window of ± 3 days for each dose; however, magrolimab doses are not to be given on consecutive days. Based on clinical, PK, and pharmacodynamic data, the CTSC decided to change dosing from twice weekly to weekly (beginning Week 3 of Cycle 1 and thereafter) with Amendment 3. Patients who are being treated under the previous Amendment may transition to the new (weekly) dosing schedule at the next cycle, or as determined by the Investigator. In the Rollover Cohort, the patient may continue the same twice-weekly schedule as the patient previously received in the Phase 1 AML study (SCI-CD47-002) or may transition to once-weekly dosing of magrolimab monotherapy at the discretion of the Investigator and with Sponsor approval. If a patient has only received Day 1 treatment for a cycle, the patient may transfer to the new dosing regimen with that cycle, for the balance of the cycle and beyond. In addition, patients in the R/R Expansion Cohort will transition from a magrolimab weekly dosing schedule to a Q2 week dosing schedule beginning in Cycle 3.

When both study drugs are given on the same visit day, magrolimab will be administered at least 1 hour after the completion of azacitidine administration.

During the first cycle (Cycle 1) (28 days) of treatment, WBC count must be  $\leq 20 \times 10^3$ /mcL prior to each magnolimab dose. Patients with WBC >  $20 \times 10^3$ /mcL can be treated with hydroxyurea (up to 4 g/day) throughout the trial to reduce the WBC to  $\leq 20 \times 10^3$ /mcL. Oral etoposide (up to 200 mg PO/day) may be given as an alternative to hydroxyurea for patients who are intolerant to hydroxyurea or cannot achieve sufficient WBC lowering on hydroxyurea.

All patients must have documented hemoglobin ≥ 9 g/dL within 24 hours prior to each of the first 2 doses of magrolimab infusion during initial treatment. Patients who do not meet these criteria must be transfused and have their hemoglobin rechecked to meet 9 g/dL prior to each of the first 2 doses of magrolimab.

Hemoglobin must be checked again 3 to 6 hours after the initiation of the first and second doses of magrolimab during initial treatment. The patient should be transfused as clinically appropriate. Investigators should consider additional hemoglobin monitoring

during the first week of treatment in patients with symptoms of anemia or at increased risk for complications of anemia.

All patients should be monitored for 1 hour post-infusion for priming, re-priming/re-escalation, and maintenance doses during Cycle 1. Post-infusion monitoring should begin after the infusion is complete. Post-infusion monitoring is not required for doses after Cycle 1, Day 22. Patients who experience any treatment-related AEs during the observation period should be further monitored, as clinically appropriate.

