# b. All TN/U Cohorts (meets i or ii):

- Previously untreated patients with MDS defined according to WHO classification, with an IPSS-R (Greenberg 2012) risk category of intermediate, high, or very high risk. Prior and concurrent therapy with hydroxyurea, oral etoposide, erythroid, and/or myeloid growth factors is allowed.
- ii. Previously untreated patients with histological confirmation of AML by WHO criteria who are ineligible for treatment with a standard cytarabine and anthracycline induction regimen due to co-morbidity, age or other factors, or who refuse such therapy.
- c. TP53 Mutant AML Subcohort: Previously untreated patients with histological confirmation of AML by WHO criteria who are ineligible for treatment with a standard cytarabine and anthracycline induction regimen due to co-morbidity, age, or other factors, or who refuse such therapy and who have presence of at least 1 TP53 gene mutation by next-generation sequencing based on local evaluation.

- d. RBC Transfusion-dependent Low-risk MDS Cohort: MDS patients with very low or low risk by IPSS-R who are RBC transfusion-dependent (requiring ≥ 2 RBC units within 8 weeks prior to screening) and meet at least one of the following:
  - Relapsed/refractory to ESA: documented non-response or response that is no longer maintained to prior ESA-containing regimen
  - ii. Intolerant to ESA: documentation of discontinuation of prior ESA-containing regimen at any time after initiation due to intolerance or adverse event
  - iii. ESA ineligible: endogenous serum erythropoietin level > 500 U/L for patients who have not been previously treated with ESAs
  - iv. Have a deletion in chromosome 5q and who are relapsed/refractory/intolerant to or ineligible for lenalidomide therapy
- e. Rollover Cohort: Patients on active magrolimab therapy on the Phase 1 AML (SCI-CD47-002) trial who are deriving clinical benefit by Investigator assessment.
- 2. WBC count ≤ 20 × 10³/mcL pre-first dose of study treatment and prior to each magrolimab dose for Cycle 1. Patients with WBC > 20 × 10³/mcL can be treated with hydroxyurea (up to 4 g/day) throughout the trial to reduce the WBC to ≤ 20 × 10³/mcL. Oral etoposide (up to 200 mg orally [PO] /day) may be given as an alternative to hydroxyurea for patients who are intolerant to hydroxyurea or cannot achieve sufficient WBC lowering on hydroxyurea.
- 3. Patient has provided informed consent.

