# Re-priming/Re-escalation for Magrolimab

Given the large CD47 antigen sink on red blood cells, patients who have a long dose delay of magrolimab are required to be re-primed with magrolimab dosing to resaturate the CD47 antigen sink.

R/R and TN/U Cohorts: For patients who had a dose delay of greater than 4 weeks for magrolimab, re-priming/re-escalation is needed with magrolimab. For patients who have not received at least one 30 mg/kg dose of magrolimab (i.e., for patients who have either not received their first dose of 30 mg/kg or patients who have received doses < 30 mg/kg), a dose delay of only 2 weeks is allowed until re-priming is needed. Table 6-1 illustrates the re-priming/re-escalation magrolimab dosing regimen and schedule of assessments.

RBC Transfusion-dependent Low-risk MDS Cohort: For patients who had a dose delay of greater than 6 weeks for magrolimab, re-priming/re-escalation is needed with magrolimab. For patients who have not received at least one 30 mg/kg dose of magrolimab, a dose delay of only 2 weeks is allowed until re-priming is needed. For patients who have not received at least one 60 mg/kg dose of magrolimab, a dose delay of 4 weeks is allowed until re-priming is needed. Table 6-1 illustrates the re-priming/re-escalation magrolimab dosing regimen and schedule of assessments.

The re-priming/re-escalation dosing regimen for magnolimab is shown below in Table 6-1.

Table 6-1. Magrolimab/Azacitidine Re-priming/Re-escalation Dosing Schedule

		Dose Schedule (Day per 28-day Cycle)		
Cohort	Drug/Dose/Route	Re-priming Cycle	Subsequent Cycles	
R/R Cohort and TN/U	Magrolimab - 1 mg/kg IV	Day 1, 4	_	
Cohort (including the TP53 Mutant TN/U AML Subcohort)	Magrolimab - 15 mg/kg IV	Day 8		
, and sassinsity	Magrolimab - 30 mg/kg IV	Day 11, 15, 22	Day 1, 15	
	Azacitidine - 75 mg/m² SC or IV b	Day 1-7	Day 1-7	
R/R MDS Magrolimab Monotherapy Cohort c	Magrolimab - 1 mg/kg IV	Day 1, 4	_	
Monotherapy Conort	Magrolimab - 15 mg/kg IV	Day 8	_	
	Magrolimab - 30 mg/kg IV	Day 11, 15, 22	Day 1, 15	
RBC Transfusion-	Magrolimab - 1 mg/kg IV	Day 1	_	
dependent Low-risk Cohort	Magrolimab - 30 mg/kg IV	Day 8, 15, 22	_	
	Magrolimab - 60 mg/kg IV a	_	Day 1	
	Azacitidine - 75 mg/m² SC or IV b	Day 1-5	Day 1-5	

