# 6.2.2. Specific Safety Management Guidelines

# 6.2.2.1. Magrolimab

For all cohorts except the RBC Transfusion-dependent Low-risk Cohort, premedication is required before administration of the first 4 doses of magrolimab with oral acetaminophen 650 to 1000 mg and oral or IV diphenhydramine 25 to 50 mg, or comparable regimen. It is also required in case of reintroduction with re-priming. For the RBC Transfusion-dependent Low-risk Cohort, premedication is required for the first 2 doses of magrolimab and the first 2 doses in case of re-introduction with re-priming. In addition, premedications are to be used to manage infusion-related reactions as described below.

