Cycle Day	sc	1	2	3	4	5	6	7	8	11	15	22	1	2	3	4	5	6	7	8	15	22	1	2	3	4	5	6	7	15
Magrolimab: Expansion Cohort t,w		Х			Х				х	Х	Х	Х	х							Х	Х	Х	Х							Х
Azacitidine v		Х	Х	Х	Х	Х	Х	Х					Х	Х	Х	Х	Х	Х	Х				Х	Х	Х	Х	Х	Х	Х	

Abbreviations: ABO = any of the 4 blood groups A, B, AB, and O comprising the ABO system; ADA = anti-drug antibodies; aPTT = activated partial thromboplastin time; C = cycle; CBC = complete blood count; CTSC = Clinical Trial Steering Committee; DAT = direct antiglobulin test; ECG = electrocardiogram; ECOG = Eastern Cooperative Oncology Group; MIN = minute; MRD = minimal residual disease; PE = physical examination; PK = pharmacokinetics; PT/INR = prothrombin time/international normalized ratio; Q2W = every 2 weeks; Q2C = every 2 cycles; Q3C = every 3 cycles; Rh = Rhesus factor; RO = receptor occupancy; R/R = relapsed/refractory; SC = screening; US = United States; W = week(s); WBC = white blood cell.

- a. Note that ± 3-day visit window does not apply to specimen collection for correlative, PK, or RO assessments in Cycles 1 and 2 refer to Table 7-6, Table 7-7, and Table 7-11 for details.
- b. First dose of magrolimab must be given within 30 days of signing informed consent.
- c. Screening pregnancy test may be used if performed within 72 hours of first dose; pregnancy tests will be conducted on Day 1 of every cycle; additional guidance is provided in Section 7.3.1.
- d. Donor chimerism only applicable to patients with prior allogeneic hematopoietic stem cell transplant.
- e. Pretreatment assessments for the initial dose (Cycle 1 Day 1) may be collected up to 72 hours before administration of either study drug (magrolimab or azacitidine); thereafter, pretreatment assessments are to be collected within 24 hours prior to study drug administration.
- f. Samples for CBC must be collected at least once per cycle. However, CBC sample collection to ensure a WBC level < 20×10³/mcL may be deferred based on Investigator assessment of the patient's WBC kinetics. Additional samples for CBC may be collected outside of the protocol-specified time points to ensure a WBC level < 20×10³/mcL.
- g. Peripheral smears will be collected prior to selected study drug infusions/injections and assessed for the presence of hemagglutination in addition to standard cell morphology assessment. Details are provided in Section 7.3.3.
- h. Time point details for correlative studies are provided in Table 7-6.

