- c. For the TN/U Expansion Cohort, RO blood samples will be collected on Day 1 of every other cycle during Cycles 3 through 7, then every 3 cycles (same day as bone marrow RO samples) after Cycle 7 through Cycle 13. For the RBC Transfusion-dependent Low-risk Cohort, RO blood samples (US only) will be collected on Day 1 of every other cycle during Cycles 3 to 7, then every 4 cycles through Cycle 19, and then starting Cycle 23 and onwards every 6 cycles (same day as bone marrow RO samples).

Table 7-14. Re-priming/Re-escalation Assessments: R/R Cohort and TN/U Cohort

	Visit Window											
Assessment	No	ne		± 3 Days								
Cycle Day (Cycle: 28 Days)	1	2	3	4	5	6	7	8	11	15	22	
CBC with differential, platelets, reticulocytes a,b	Х	Х		Х				Х	Х	Х	Х	
Peripheral blood smear a,c	Х	Х						Х		Х		
Serum or plasma chemistry a	Х	Х						Х		Х	Х	
Serum uric acid, phosphorus a	Х	Х						Х		Х		
Haptoglobin, D-dimer, thrombin, fibrinogen a	Х	Х						Х		Х		
PT/INR, aPTT a								Х				
Anti-drug antibodiesd	Х											
CD47 RO blood e	Х							Х	Х	Х		
ECOG a	Х							Х		Х		
Vital signs f	Х	Х						Х		Х		
Physical examination a,g	Х							Х		Х		
Adverse events	_										-	
Concomitant medications	_										-	
Magrolimab premedication	Х			Х				Х	Х			
Magrolimab: Re-priming/re-escalation h	Х			Х				Х	Х	Х	Х	
Azacitidine h,i	Х	Х	Х	Х	Х	Х	Х					

Abbreviations: aPTT = activated partial thromboplastin time; CBC = complete blood count; ECOG = Eastern Cooperative Oncology Group; IV = intravenous; PE = physical examination; PT/INR = prothrombin time/international normalized ratio; Rh = Rhesus factor; RO = receptor occupancy; SC = subcutaneous; US = United States; WBC = white blood cell.

- a. Pretreatment assessments for the initial dose (Cycle 1 Day 1) may be collected up to 72 hours before study drug administration; thereafter, pretreatment assessments are to be collected within 24 hours prior to study drug administration.
- b. Samples for CBC must be collected at least once per cycle. However, CBC sample collection to ensure a WBC level < 20 × 10^3/mcL may be deferred, based on Investigator assessment of the patient's WBC kinetics. Additional samples for CBC may be collected outside of the protocol-specified time points to ensure a WBC level < 20 × 10^3/mcL.

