### 7.3.2. Complete Blood Counts

Samples for CBCs should be collected per the Schedule of Assessments in Section 7.1, and must be collected at least once per cycle. However, CBC sample collection to ensure a WBC level  $\leq 20 \times 10^3$ /mcL may be deferred, based on Investigator assessment of the patient's WBC kinetics. Additional samples for CBC may be collected outside of the protocol-specified time points to ensure a WBC level  $\leq 20 \times 10^3$ /mcL.

All participants must have a documented hemoglobin ≥ 9 g/dL prior to administering the first 2 doses of magrolimab. Participants who do not meet these criteria must be transfused and have their hemoglobin rechecked to meet the minimum hemoglobin threshold prior to administering each of the first 2 doses of magrolimab.

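### Section 6.1.1 does not say whether the waiver of post-infusion observation after Cycle 1 Day 22 reaches re-priming doses (minor, patient safety only)

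*Protocol*

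**What the plan says.** Section 6.1.1 sets the observation rule in one short paragraph. Its first sentence asks for 1 hour of observation after priming doses and after "re-priming/re-escalation, and maintenance doses during Cycle 1". The waiver follows in the same paragraph: "Post-infusion monitoring is not required for doses after Cycle 1, Day 22".

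The re-priming subsection of 6.1.1 gives the trigger for the R/R and TN/U cohorts: "For patients who had a dose delay of greater than 4 weeks for magrolimab, re-priming/re-escalation is needed with magrolimab". In the low-risk MDS cohort the limit is 6 weeks, or 4 weeks before the first 60 mg/kg dose. In all these cohorts it is 2 weeks before the first 30 mg/kg dose. Table 6-1 schedules the course on Days 1, 4, 8, 11, 15 and 22 (R/R, TN/U) or Days 1, 8, 15 and 22 (low-risk MDS), under the column title Re-priming Cycle.

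Elsewhere the protocol deals with re-priming explicitly. On premedication, Section 6.2.2.1 says "It is also required in case of reintroduction with re-priming", and it adds a separate provision for the low-risk cohort.

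Two neighbouring rules are relevant to tidying. Inclusion criterion 2 sets the white-cell limit "pre-first dose of study treatment and prior to each magrolimab dose for Cycle 1", while Section 7.3.2 says the blood count that checks it "may be deferred, based on Investigator assessment of the" patient's white-cell kinetics. Criterion 7 and Section 6.1.1 require hemoglobin of at least 9 g/dL within 24 hours before each of the first two doses. The pretreatment footnotes of Tables 7-1 (e) and 7-2 (d) allow assessments up to 72 hours before the first dose.

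**The concern.** The observation rule grants something to re-priming doses that the waiver, read literally, takes away. Re-priming happens only after a delay of weeks, so measured from first treatment almost all of it lies beyond Cycle 1 Day 22. A site could also attach the Cycle 1 limit to the whole list of dose types instead of to maintenance doses alone, and it would reach the same result.

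The protocol gives a reason to care. Re-priming exists to resaturate CD47 on red cells after a long gap, and premedication becomes mandatory again at that point. The hemoglobin recheck 3 to 6 hours after the start of the first two doses applies only to initial treatment, so it does not stand in for observation at re-priming. At stake is whether sites handle these doses alike. No efficacy or safety estimate depends on it.

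**Working it through.** The plan gives no figure to reproduce, so the check is date arithmetic followed by a comparison of readings.

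**Inputs.** Dose days are from Tables 3-1, 3-2 and 3-3, delay limits from the re-priming subsection of 6.1.1, and course days from Table 6-1. All are nominal days, without visit windows.

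**Formula.** With last dose on day L and allowed delay D days, the earliest re-priming day is S = L + D + 1. A dose on day k of the course falls on S + k − 1.

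| Case | L | D | S | Course falls on | After Day 22 |
|---|---|---|---|---|---|
| R/R, TN/U: first 30 mg/kg given | 11 | 28 | 40 | 40, 43, 47, 50, 54, 61 | 6 of 6 |
| Low-risk: first 30 mg/kg given, no 60 mg/kg | 8 | 28 | 37 | 37, 44, 51, 58 | 4 of 4 |
| Low-risk: first 60 mg/kg given | 29 | 42 | 72 | 72, 79, 86, 93 | 4 of 4 |
| R/R, TN/U: only the Day 1 dose given | 1 | 14 | 16 | 16, 19, 23, 26, 30, 37 | 4 of 6 |
| Low-risk: only the Day 1 dose given | 1 | 14 | 16 | 16, 23, 30, 37 | 3 of 4 |

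Counting the delay from the missed dose instead moves the start later. In the first row the next dose is due on Day 15, so S = 15 + 28 + 1 = 44.

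**Readings for a patient who has had 30 mg/kg.**

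- Waiver taken literally, with Day 22 counted from first treatment: 0 of 6 (or 0 of 4) re-priming doses observed.
- Cycle 1 limit attached to the whole list, with cycles counted from first treatment: also none, because Days 40 and 37 lie beyond the first 28-day cycle.
- Specific mention of re-priming prevails over the general waiver: all 6 (or 4) observed.
- Day 22 counted within the re-priming cycle: all 6 (or 4) observed, because the last re-priming dose falls on Day 22 and not after it. Table 7-14 footnote a and Table 7-15 footnote b lend this some support by labelling the first re-priming dose as Cycle 1 Day 1: "Pretreatment assessments for the initial dose (Cycle 1 Day 1) may be collected up to 72 hours before study drug administration". The Table 6-1 column title points the other way.

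The choice of reading therefore moves observation between 0 and 6 hours per course (0 and 4 in low-risk MDS). The protocol does not say how often re-priming occurs, so a trial-wide total cannot be given.

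**Tidying points.** The deferral wording appears in 7.3.2 and again in the blood-count footnotes of Tables 7-1 (f), 7-2 (e) and 7-3 (e). For example, Table 7-1 says "may be deferred based on Investigator assessment of the" patient's white-cell kinetics. None of these excludes Cycle 1. For hemoglobin, the footnote window exceeds the rule by 72 − 24 = 48 hours at the first dose. Table 7-3 has the same 72-hour footnote but corrects it in footnote x; Tables 7-1 and 7-2 have no such note.

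**The case against.** The strongest reply is that a sensible reader would not let a general waiver empty a specific provision in the same paragraph, and that the re-priming tables partly support counting Day 22 afresh. Either reading removes the conflict. The waiver also only says observation is not required, so a site that observes every re-priming dose complies with both sentences. Other protection remains: premedication, vital signs within 30 minutes after each infusion (Table 7-14 footnote f, Table 7-15 footnote g), and a 24-hour frame for assessing infusion reactions (Section 6.2.2.1). All of this stands, and it is why the point is an ambiguity rated minor. It does not close the point, because 6.1.1 states neither harmonising reading, whereas the premedication rules show the protocol can name re-priming when it means to.

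On the tidying points, a reader might infer that a 72-hour-old hemoglobin is acceptable at the first dose. The documents do not support that: Sections 4.1.1, 6.1.1 and 6.2.2.1 make 24 hours mandatory, the footnote is a permissive outer limit, and one sample inside 24 hours meets both. Tables 7-1 to 7-3 also schedule a blood count on every Cycle 1 magrolimab day, and all three are marked closed to enrollment.

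A reader might also count the deferral wording in Tables 7-4, 7-14 and 7-15 as further conflicts with the Cycle 1 white-cell rule. Table 7-4 covers azacitidine holds. Azacitidine delay is barred in the first cycle of TN/U Expansion (6.2.1.2), and 6.2.1.1 refers Cycle 1 patients in that cohort and the low-risk cohort back to that cycle's own schedule. The other two are re-priming tables, and re-priming cannot be placed outside Cycle 1 for the observation point and inside it for this one. Only a rare early delay would bring them into conflict.

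**Conclusion.** The point holds as a minor drafting ambiguity affecting patient safety only. Section 6.1.1 leaves open whether re-priming doses are observed, and for patients who have had 30 mg/kg the answer swings between none and all of a 6-dose or 4-dose course.

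A reader might go further and infer that the protocol withdraws observation from re-priming. The text does not establish that: the counts of 6 of 6 and 4 of 4 hold only if Day 22 is counted from first treatment and the waiver overrides the specific mention. The dates also assume nominal dosing days and delay counted from the last dose.

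The point stays live after enrollment closes, since any patient still on treatment can have a long delay. The blood-count and hemoglobin wording is optional tidying.

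**What to change.** Reword 6.1.1 so that the Cycle 1 limit attaches to maintenance doses only and the waiver carries an exception. Suggested text: *Observe every patient for 1 hour after the end of infusion for each priming dose, for each re-priming/re-escalation dose whenever it is given, and for each maintenance dose in Cycle 1. After Cycle 1 Day 22 no observation is needed, except for re-priming/re-escalation doses.*

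The cost is one clause at the next amendment and 1 hour of observation per re-priming dose: up to 6 hours per course in the R/R and TN/U cohorts and 4 in low-risk MDS.

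Optional in the same amendment, and useful only if a patient is still in, or enters, Cycle 1:

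- State in 7.3.2 and in Table 7-1 footnote f, Table 7-2 footnote e and Table 7-3 footnote e that the blood-count deferral does not apply before Cycle 1 magrolimab doses.
- Carry the 24-hour hemoglobin note (Table 7-3 footnote x) into Tables 7-1 and 7-2, with Days 1 and 4 as the dose days.

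Neither adds a procedure, because 6.1.1 already requires the white-cell level and the hemoglobin check.
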